16.1.2 Response Review

Since therapeutic efficacy is a stated primary objective for the Phase II portion of this study, all sites Phase II participants' responses are subject to review by MSK's Therapeutic Response Review Committee (TRRC). Radiology, additional lab reports and possibly bone marrow biopsies and/or aspirates will need to be obtained from the participating sites for MSK TRRC review and confirmation of response assessment. These materials must be sent to MSK promptly upon request.

16.2 Data and Safety Monitoring

The Data and Safety Monitoring (DSM) Plans at Memorial Sloan-Kettering Cancer Center were approved by the National Cancer Institute in September 2001. The plans address the new policies set forth by the NCI in the document entitled "Policy of the National Cancer Institute for Data and Safety Monitoring of Clinical Trials" which can be found at:

<http://cancertrials.nci.nih.gov/researchers/dsm/index.html>. The DSM Plans at MSKCC were established and are monitored by the Office of Clinical Research. The MSKCC Data and Safety Monitoring Plans can be found on the MSKCC Intranet at:
<http://inside2/clinresearch/Documents/MSKCC%20Data%20and%20Safety%20Monitoring%20Plans.pdf>.

There are several different mechanisms by which clinical trials are monitored for data, safety and quality. There are institutional processes in place for quality assurance (e.g., protocol monitoring, compliance and data verification audits, therapeutic response, and staff education on clinical research QA) and departmental procedures for quality control, plus there are two institutional committees that are responsible for monitoring the activities of our clinical trials programs. The committees: Data and Safety Monitoring Committee (DSMC) for Phase I and II clinical trials, and the Data and Safety Monitoring Board (DSMB) for Phase III clinical trials, report to the Center's Research Council and Institutional Review Board.

MEMORIAL SLOAN-KETTERING CANCER CENTER IRB PROTOCOL

IRB#: 14-140 A (7)

During the protocol development and review process, each protocol will be assessed for its level of risk and degree of monitoring required. Every type of protocol (e.g., NIH sponsored, in-house sponsored, industrial sponsored, NCI cooperative group, etc.) will be addressed and the monitoring procedures will be established at the time of protocol activation.

16.3 Regulatory Documentation

Prior to implementing this protocol at MSKCC, the protocol, informed consent form, HIPAA authorization and any other information pertaining to participants must be approved by the MSKCC Institutional Review Board/Privacy Board (IRB/PB). Prior to implementing this protocol at the participating sites, approval for the MSKCC IRB/PB approved protocol must be obtained from the participating site's IRB.

The following documents must be provided to MSKCC before the participating site can be initiated and begin enrolling participants:

- Participating Site IRB approval(s) for the protocol, appendices, informed consent form and HIPAA authorization
- Participating Site IRB approved consent form
- Participating Site 1572
- Participating Site IRB membership list
- Participating Site IRB's Federal Wide Assurance number and OHRP Registration number
- Curriculum vitae and medical license for each investigator and consenting professional
- Documentation of Human Subject Research Certification training for investigators and key staff members at the Participating Site
- Good Clinical Practice Training for the Principal Investigator and Co-Investigator
- Conflict of Interest forms for Participating Site Investigators on the 1572
- Participating site laboratory certifications and normals

Upon receipt of the required documents, MSKCC will formally contact the site and grant permission to proceed with enrollment.

Participating sites that are consulting and/or conducting specimen or data analysis should submit this protocol to their IRB according to local guidelines. Copies of any site IRB correspondence should be forwarded to MSKCC. Participating sites that are conducting specimen analysis must provide a 1572 to MSKCC.

16.3.1 Amendments

Each change to the protocol document must be organized and documented by MSKCC and first approved by the MSKCC IRB/PB. Upon receipt of MSKCC IRB/PB approval, MSKCC will immediately distribute all non-expedited amendments to the participating sites, for submission to their local IRBs.

Participating sites must obtain approval for all non expedited amendments from their IRB within 45 calendar days of MSKCC IRB/PB releasing the protocol. If the amendment is the result of a safety issue or makes eligibility criteria more restrictive, sites will not be permitted to continuing enrolling new participants until the participating site IRB approval has been granted.

MEMORIAL SLOAN-KETTERING CANCER CENTER IRB PROTOCOL

IRB#: 14-140 A (7)

The following documents must be provided to MSKCC for each amendment within the stated timelines:

- Participating Site IRB approval
- Participating Site IRB approved informed consent form and HIPAA authorization

16.3.2 Additional IRB Correspondence

Continuing Review Approval

The Continuing Review Approval letter from the participating site's IRB and the most current approved version of the informed consent form should be submitted to MSKCC within 7 days of expiration. Failure to submit the re-approval in the stated timeline will result in suspension of new participant enrollment.

Deviations and Violations

A protocol deviation on this study is defined as a request to treat a research participant who requires alteration in their study plan. If a deviation from this protocol is proposed for a potential or existing participant at MSKCC or a participating site, approval from the MSKCC IRB/PB is required prior to the action. Participating sites should contact the MSKCC PI who will in turn seek approval from the MSKCC IRB/PB. Deviation requests from eligibility criteria will not be permitted for research participants.

A protocol violation is any change or departure from the research protocol that occurred without prior approval from the MSKCC IRB/PB. For protocol violations that are identified after they occur, the participating site should report to MSKCC within 14 days of learning of the event. The MSKCC PI will in turn report the violation to the MSKCC IRB/PB.

Participating sites should report deviations and violations to their institution's IRBs as soon as possible per that site's institutional guidelines. Approvals/acknowledgments from the participating site IRB for protocol deviations and violations should be submitted to MSKCC as received.

Other correspondence

Participating sites should submit other correspondence to their institution's IRB according to local guidelines, and submit copies of that correspondence to MSKCC.

16.3.3 Regulatory Documentation Submission for Participating Sites

Participating sites should submit all aforementioned regulatory documentation to MSK via the Multicenter Office at the e-mail provided below. Submissions should include the provided Participating Site Submission Form as a cover page listing all enclosed documents.

Regulatory Contact:

Email: [contact] to the attention of 14-140 Document Submission

For questions regarding regulatory documentation submissions, please call [contact].

MEMORIAL SLOAN-KETTERING CANCER CENTER IRB PROTOCOL

IRB#: 14-140 A (7)

For protocol related questions, please contact your MSK Study Coordinator.

16.4 Document maintenance

The MSKCC PI and the Participating Site PI will maintain adequate and accurate records to enable the implementation of the protocol to be fully documented and the data to be subsequently verified.

The participating sites will ensure that all participating site IRB correspondence (IRB approval letters referencing protocol version date and amendment number, IRB approved protocol, appendices, informed consent forms, deviations, violations, and approval of continuing reviews) is maintained in the regulatory binder on site and sent to MSKCC. The regulatory binder on site will be reviewed by the MSKCC designated study monitor at monitoring visits.

A regulatory binder for each site will also be maintained at MSKCC; this binder may be paper or electronic.

After study closure, the participating site will maintain all source documents and study related documents for 7 years.

16.5 Noncompliance

If a participating site is noncompliant with the protocol document, accrual privileges may be suspended and/or contract payments may be withheld, until the outstanding issues have been resolved.

17.0 PROTECTION OF HUMAN SUBJECTS

Participation in this trial is voluntary. The patients will be explained the extent of the risks, benefits, toxicities/side effects, alternatives/options for treatment, financial costs/burdens, and the voluntary nature of the study. All patients will be required to sign a statement of informed consent, which must conform to IRB guidelines.

Inclusion of Women and Minorities: Memorial Sloan-Kettering Cancer Center has filed forms: HHS 441 (civil rights), HHS (handicapped individual), 639-A (sex discrimination), and 680 (age discrimination); we also take due notice of the NIH policy concerning inclusion of women and minorities in clinical research populations. Patients of all races, both male and female, will be accepted into the protocol. The proposed study population is as described in section 6.0 and 7.0.

Exclusion of Lactating or Pregnant Women: Lactating and pregnant women are also excluded because of potential anti-proliferative effects of BGJ398 and/or imatinib that may be harmful to the developing fetus or nursing infant.

Inclusion of Children in Research: This protocol/project does not include patients younger than the age of 18. Although sarcomas are the most common solid tumor in children, pediatric GISTs are relatively rare. In addition, pediatric GISTs often do not respond to imatinib as they tend to not have

MEMORIAL SLOAN-KETTERING CANCER CENTER IRB PROTOCOL

IRB#: 14-140 A (7)

mutations in cKIT. Pediatric GIST patients would be better served enrolling on clinical trials specifically designed for the genetic abnormalities of their tumor.

Benefits: It is possible that this treatment will result in shrinkage of the tumor or in a stabilization of an otherwise progressing disease. It is not known, of course, whether these or any other favorable events will occur. It is not known whether this treatment will affect the overall survival of the patients.

Costs: The patient will be responsible for the costs of standard medical care, including all drug administration fees and all hospitalizations, even for complications of treatment. BGJ398 and Imatinib will be provided to the patient without charge. Research-only biopsies and laboratory tests will not be charged to the patient. Research testing performed on tissue will not be charged to the patient.

Incentives: No incentives will be offered to patients/subjects for participation in the study.

Alternatives: For patients with locally advanced and/or metastatic GIST alternative treatments may include imatinib off study per standard of care or other clinical trials.

Confidentiality: Every effort will be made to maintain patient confidentiality. Research and hospital records are confidential. Patient's name or any other personally identifying information will not be used in reports or publications resulting from this study. The Food and Drug Administration or other authorized agencies (e.g., qualified monitors from MSKCC or collaborating institutions) may review patients' records and pathology slides, as required.

17.1 Privacy

MSKCC's Privacy Office may allow the use and disclosure of protected health information pursuant to a completed and signed Research Authorization form. The use and disclosure of protected health information will be limited to the individuals described in the Research Authorization form. A Research Authorization form must be completed by the Principal Investigator and approved by the IRB and Privacy Board (IRB/PB).

17.2 Serious Adverse Event (SAE) Reporting

An adverse event is considered serious if it results in ANY of the following outcomes:

- Death
- A life-threatening adverse event
- An adverse event that results in inpatient hospitalization or prolongation of existing hospitalization
- A persistent or significant incapacity or substantial disruption of the ability to conduct normal life functions
- A congenital anomaly/birth defect
- Important Medical Events (IME) that may not result in death, be life threatening, or require hospitalization may be considered serious when, based upon medical judgment,

MEMORIAL SLOAN-KETTERING CANCER CENTER IRB PROTOCOL

IRB#: 14-140 A (7)

they may jeopardize the patient or subject and may require medical or surgical intervention to prevent one of the outcomes listed in this definition

Note: Hospital admission for a planned procedure/disease treatment is not considered an SAE.

SAE reporting is required as soon as the participant signs consent. SAE reporting is required for 30-days after the participant's last investigational treatment or intervention. Any events that occur after the 30-day period and that are at least possibly related to protocol treatment must be reported.

If an SAE requires submission to the IRB office per IRB SOP RR-408 'Reporting of Serious Adverse Events', the SAE report must be sent to the IRB within 5 calendar days of the event. The IRB requires a Clinical Research Database (CRDB) SAE report be submitted electronically to the SAE Office as follows:

For IND/IDE trials: Reports that include a Grade 5 SAE should be sent to [contact]. All other reports should be sent to [contact].

For all other trials: Reports that include a Grade 5 SAE should be sent to [contact]. All other reports should be sent to [contact].

The report should contain the following information:

Fields populated from CRDB:

- Subject's initials
- Medical record number
- Disease/histology (if applicable)
- Protocol number and title

Data needing to be entered:

- The date the adverse event occurred
- The adverse event
- The grade of the event
- Relationship of the adverse event to the treatment (drug, device, or intervention)
- If the AE was expected
- The severity of the AE
- The intervention
- Detailed text that includes the following
 - A explanation of how the AE was handled
 - A description of the subject's condition
 - Indication if the subject remains on the study
- If an amendment will need to be made to the protocol and/or consent form

MEMORIAL SLOAN-KETTERING CANCER CENTER
IRB PROTOCOL

IRB#: 14-140 A (7)

- If the SAE is an Unanticipated Problem

The PI's signature and the date it was signed are required on the completed report.

For IND/IDE protocols:

The CRDB SAE report should be completed as per above instructions. If appropriate, the report will be forwarded to the FDA by the SAE staff through the IND Office

17.2.1 Reporting to Novartis by MSKCC

Reporting Responsibility:

Any serious adverse events that occur from the first dose of study treatment until 30 days after receiving the last dose of study medication, whether or not related to the study drug, must be reported by the investigator at MSKCC to Novartis. In addition, any SAEs that occur as a result of protocol specific diagnostic procedures or interventions must also be reported.

Each serious adverse event (but not pregnancies) must be reported by the investigator at MSKCC to Novartis within 24 hours of learning of its occurrence, even if it is not felt to be treatment-related. Follow-up information about a previously reported serious adverse event must also be reported to Novartis within 24 hours of receiving it. If the serious adverse event has not been previously documented (new occurrence) and it is thought to be related to study drug (or therapy), the Medical Safety Expert of the Clinical Safety & Epidemiology (CS&E) Department may contact the investigator to obtain further information. If warranted, an investigator alert may be issued, to inform all investigators involved in any study with the same drug (or therapy) that this serious adverse event has been reported.

Reporting Procedures:

The MSKCC principal investigator has the obligation to report all serious adverse events to the MSKCC IRB, FDA (all correspondence with the FDA must go through the MSKCC IND Office) and Novartis Pharmaceuticals Clinical Safety & Epidemiology (CS&E) Department.

SAEs will be reported to Novartis once reported to the MSKCC IRB using the MSKCC CRDB SAE Report Form.

All serious adverse events must be reported by facsimile within 24 hours of learning of the occurrence to the local Novartis Clinical Safety & Epidemiology (CS&E) Department. [contact].

The investigator must then ensure that the form and coversheet are accurately and fully completed with follow-up information and fax those to Novartis CS&E Department within 5 calendar days of receiving it. The original and the duplicate copies of the CRDB SAE Report Form, Novartis SAE coversheet, and the fax confirmation sheet must be retained at MSKCC.

Follow-up information should describe whether the event has resolved or continues, if and how it was treated, whether the blind was broken or not, and whether the patient continued or discontinued study participation.

MEMORIAL SLOAN-KETTERING CANCER CENTER
IRB PROTOCOL

IRB#: 14-140 A (7)

17.3 Serious Adverse Event (SAE) Reporting for Participating Sites

Responsibility of Participating Sites

- Participating sites are responsible for reporting all SAEs to their local IRB per local guidelines. Local IRB SAE approvals/acknowledgments must be sent to MSK upon receipt.
- Participating sites are responsible for submitting the SAE Report Form to MSK within 48 hours of learning of the event.
- When a death is unforeseen and indicates participants or others are at increased risk of harm, participating sites should notify the MSK PI as soon as possible but within 24 hours of the time the site becomes aware of the event.

SAE contact information for the Coordinating Center is listed below:

Multicenter Trials Core Staff
MSKCC Clinical Trials Office
[name]
New York, NY 10065
(F) [contact]
Email: [contact]

[name]
Memorial Sloan Kettering Cancer Center
[name]
New York, NY 10065
(O) [contact] (F) [contact]
Email: [contact]

Responsibility of MSKCC

- The MSKCC Research Staff is responsible for submitting all SAEs to the MSKCC IRB/PB as specified in 17.2 and to Novartis as described in 17.2.1
- The MSKCC PI is responsible for informing all participating sites about all deaths and unexpected SAEs that are either possibly, probably, or definitely related to the study intervention within 30 days of receiving the stamped SAE from the MSKCC IRB/PB.
- Any report pertaining to a grade 5 event will be distributed to the participating sites as soon as possible.

17.4 Safety Reports

MSK must submit external safety reports to the MSK IRB/PB according to institutional guidelines. All external safety reports will be made available to the participating sites. For those safety reports that require an amendment, the participating sites will receive a special alert.

Participating sites are responsible for submitting safety reports to their local IRB per their local IRB guidelines. All local IRB approvals/acknowledgments of safety reports must be sent to MSK upon receipt.

MEMORIAL SLOAN-KETTERING CANCER CENTER IRB PROTOCOL

IRB#: 14-140 A (7)

18.0 INFORMED CONSENT PROCEDURES

Before protocol-specified procedures are carried out, consenting professionals will explain full details of the protocol and study procedures as well as the risks involved to participants prior to their inclusion in the study. Participants will also be informed that they are free to withdraw from the study at any time. All participants must sign an IRB/PB-approved consent form indicating their consent to participate. This consent form meets the requirements of the Code of Federal Regulations and the Institutional Review Board/Privacy Board of this Center. The consent form will include the following:

1. The nature and objectives, potential risks and benefits of the intended study.
2. The length of study and the likely follow-up required.
3. Alternatives to the proposed study. (This will include available standard and investigational therapies. In addition, patients will be offered an option of supportive care for therapeutic studies.)
4. The name of the investigator(s) responsible for the protocol.
5. The right of the participant to accept or refuse study interventions/interactions and to withdraw from participation at any time.

Before any protocol-specific procedures can be carried out, the consenting professional will fully explain the aspects of patient privacy concerning research specific information. In addition to signing the IRB Informed Consent, all patients must agree to the Research Authorization component of the informed consent form.

Each participant and consenting professional will sign the consent form. The participant must receive a copy of the signed informed consent form.

18.1 Informed Consent Procedures for Participating Sites

The investigators listed on the Consenting Professionals Lists at each participating site may obtain informed consent and care for the participants according to good clinical practice and protocol guidelines.

A note will be placed in the medical record documenting that informed consent was obtained for this study, and that the participant acknowledges the risk of participation.

MEMORIAL SLOAN-KETTERING CANCER CENTER
IRB PROTOCOL

IRB#: 14-140 A (7)

20.0 APPENDICES

Appendix A: KPS-ECOG Conversion Chart

Appendix B: Patient Oral Medication Diary

Appendix C: LIST OF CYP3A4 and CYP2B6 INHIBITORS AND INDUCERS (Imatinib)

Appendix D: List of concomitant medications to be used with caution with BGJ398

Appendix E: List of prohibited medications with BGJ398

Appendix F: List of select High-phosphorous foods and suggested alternatives

Appendix G: Ophthalmology Exam Forms

**MEMORIAL SLOAN-KETTERING CANCER CENTER
IRB PROTOCOL**

IRB#: 14-140 A (7)

Appendix A: Performance Status Criteria

ECOG Performance Status Scale		Karnofsky Performance Scale	
Grade	Descriptions	Percent	Description
0	Normal activity. Fully active, able to carry on all pre-disease performance without restriction.	100	Normal, no complaints, no evidence of disease.
		90	Able to carry on normal activity; minor signs or symptoms of disease.
1	Symptoms, but ambulatory. Restricted in physically strenuous activity, but ambulatory and able to carry out work of a light or sedentary nature (e.g., light housework, office work).	80	Normal activity with effort; some signs or symptoms of disease.
		70	Cares for self, unable to carry on normal activity or to do active work.
2	In bed <50% of the time. Ambulatory and capable of all self-care, but unable to carry out any work activities. Up and about more than 50% of waking hours.	60	Requires occasional assistance, but is able to care for most of his/her needs.
		50	Requires considerable assistance and frequent medical care.
3	In bed >50% of the time. Capable of only limited self-care, confined to bed or chair more than 50% of waking hours.	40	Disabled, requires special care and assistance.
		30	Severely disabled, hospitalization indicated. Death not imminent.
4	100% bedridden. Completely disabled. Cannot carry on any self-care. Totally confined to bed or chair.	20	Very sick, hospitalization indicated. Death not imminent.
		10	Moribund, fatal processes progressing rapidly.
5	Dead.	0	Dead.

MEMORIAL SLOAN-KETTERING CANCER CENTER
IRB PROTOCOL

IRB#: 14-140 A (7)

Appendix B: Pill Diary for IRB #14-140: SCHEDULE A

Name: _____

MRN: _____

A phase Ib/II study of BGJ398 in combination with imatinib mesylate in patients with untreated advanced gastrointestinal stromal tumor (GIST)

	Total Daily Dose	Capsule Strength (mg)	Number of Capsule Given	Pill Bottles Returned?	Number of Capsule Returned
Imatinib				Y or N	
BGJ398				Y or N	

(Above to be Completed by RN)

PLEASE FILL OUT AND BRING THIS SHEET AT YOUR NEXT VISIT.

SPECIAL INSTRUCTIONS

- Imatinib should be taken orally with food. BGJ398 should be taken in the morning 2 hours after a light breakfast. No food should be consumed for 1 hour after taking the capsule. Both should be taken with a large glass of water (8oz).
- Do not chew or crush the capsule .
- Do not drink grapefruit juice or take herbal supplements such as St. John’s Wort while taking these medications.
- Take imatinib once a day, no less than twelve hours between each dose. If a dose of imatinib is missed, please take the dose as soon as possible, but **only** if there are **12 or more** hours remaining before the next dose.
 - a. If the dose is due in less than 12 hours, **skip** the missed dose and take the next dose as scheduled.
- Take BGJ398 once a day in the morning. If a dose of BGJ398 is missed, take as soon as possible **within 2 hours** of the missed dose. If 2 hours passes, **skip** the missed dose and take the next dose as scheduled.
- If vomiting occurs after taking either imatinib or BGJ398, even if it appears the whole capsule has been regurgitated, do not take a replacement dose. Resume at the next scheduled dose.
 - a. If consistent vomiting occurs please notify the study investigator

All missed doses should be recorded in this pill diary.

MEMORIAL SLOAN-KETTERING CANCER CENTER
IRB PROTOCOL

IRB#: 14-140 A (7)

DAY	MEDICATION	DATE	TIME	NUMBER of ___ mg capsules taken	NUMBER of ___ mg capsules taken
Example	Imatinib	01/01/2010	9:00 AM or PM	1	
	BGJ398		9:00 AM		1
Day 1	Imatinib				
	BGJ398				
Day 2	Imatinib				
	BGJ398				
Day 3	Imatinib				
	BGJ398				
Day 4	Imatinib				
	BGJ398				
Day 5	Imatinib				
	BGJ398				
Day 6	Imatinib				
	BGJ398				
Day 7	Imatinib				
	BGJ398				
Day 8	Imatinib				
	BGJ398				
Day 9	Imatinib				
	BGJ398				
Day 10	Imatinib				
	BGJ398				
Day	Imatinib				

MEMORIAL SLOAN-KETTERING CANCER CENTER
IRB PROTOCOL

IRB#: 14-140 A (7)

11	BGJ398				
Day 12	Imatinib				
	BGJ398				
Day 13	Imatinib				
	BGJ398				
Day 14	Imatinib				
	BGJ398				
Day 15	Imatinib				
	BGJ398				
Day 16	Imatinib				
	BGJ398				
Day 17	Imatinib				
	BGJ398				
Day 18	Imatinib				
	BGJ398				
Day 19	Imatinib				
	BGJ398				
Day 20	Imatinib				
	BGJ398				
Day 21	Imatinib				
	BGJ398				
Day 22	Imatinib				
	BGJ398				
Day 23	Imatinib				
	BGJ398				
Day 24	Imatinib				
	BGJ398				
Day	Imatinib				

MEMORIAL SLOAN-KETTERING CANCER CENTER
 IRB PROTOCOL

IRB#: 14-140 A (7)

25	BGJ398				
Day 26	Imatinib				X
	BGJ398				X
Day 27	Imatinib				X
	BGJ398				X
Day 28	Imatinib				X
	BGJ398				X

Patient Signature: _____

Date: _____

Consenting Professional/Research RN Signature: _____

Date: _____

Consenting Professional/Research RN Comments:

MEMORIAL SLOAN-KETTERING CANCER CENTER
IRB PROTOCOL

IRB#: 14-140 A (7)

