5.2.3 Administration of BGJ398

BGJ398 will be taken orally, using treatment schedule A (once a day for 21 days on, 7 days off) or treatment schedule B (once daily for 7 days on, 21 days off) repeating in 28 day cycles. Patients should be instructed to take the daily dose of BGJ398 in the morning, at approximately the same time each day (24 ± 2 hour interval). Patients should consume a light breakfast each day (e.g., non-grapefruit-based juice, toast and jam). This should be followed by a 2 hour fast, after which the doses of study drug should be taken. Patients should continue to fast for 1 hour after the administration of study drug.

BGJ398 should be taken with a large glass of water (~250 mL) and consumed over as short a time as possible. Patients should be instructed to swallow the capsules whole and not chew them. If for any reason a breakfast was not consumed prior to taking the dose the patient should take the dose with a full glass of water, and continue to fast for an hour after taking the dose. If the patient forgets to take the scheduled dose in the morning, he/she should not take the dose more than 2 hours after the usual time and should continue treatment the next day. Any doses that are missed should be skipped altogether and should not be replaced or made up at the next scheduled dosing.

If vomiting occurs following the dosing of study drug, re-dosing is not permitted that same day. Dosing should resume the next day. BGJ398 is characterized by pH-dependent solubility, and therefore, medicinal products that alter the pH of the upper gastro-intestinal tract may alter the solubility of both compounds, and limit bioavailability. These agents include, but are not limited to, proton-pump inhibitors (e.g., omeprazole), H₂-antagonists (e.g., ranitidine) and antacids. Therefore, BGJ398 should be dosed at least 2 hours before or 10 hours after dosing with a gastric protection agent. Patients must avoid consuming Seville oranges or juice, grapefruit, grapefruit juice, grapefruit hybrids, or pummelos from 7 days prior to the first dose of study medication through the end of study participation. This is due to a potential CYP3A4 interaction with study medication. Normal oranges and orange juice are allowed.

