9.0 TREATMENT/INTERVENTION PLAN

Treatment will be administered on an outpatient basis. Reported adverse events and potential risks are described in Section 11. Appropriate dose modifications of imatinib and BGJ398 are described in section 9.2. No investigational or commercial agents or therapies other than those described below may be administered with the intent to treat the patient's malignancy.

MEMORIAL SLOAN-KETTERING CANCER CENTER IRB PROTOCOL

IRB#: 14-140 A (7)

Imatinib will be self administered orally by the patient on a daily basis throughout the treatment cycle. The standard treatment dose is 400 mg PO QD. 400 mg capsule will be used unless otherwise specified by the treating physician. BGJ398 will be taken at the RP2D and treatment schedule chosen from the Phase Ib portion of the trial. The RP2D selected may be lower than the MTD based on PK data and clinical tolerance beyond Cycle 1. BGJ398 is taken daily for a duration determined by the treatment schedule appropriate for the given dose level. In the event of dose delays of BGJ398, Day 1 of the following cycle will be defined as the day that BGJ398 is restarted. A pill diary for both medications will be provided and recorded (Appendix B). This will be used to assure compliance with the regimen.

On the Phase Ib portion, the timing of pharmacokinetic sample collections will be dependent on the treatment schedule onto which that patient is enrolled. For treatment schedule A pharmacokinetic samples will be drawn on Cycle 1, Day 1 at the following timepoints: 0, 1, 2, 4, 6, 8, and 24 hrs; and Cycle 1, Day 21 at the following timepoints: 0, 1, 2, 4, 6, and 8 hours. For treatment schedule B pharmacokinetic samples will be drawn on Cycle 1, Day 1 at the following timepoints: 0, 1, 2, 4, 6, 8, and 24 hrs; Cycle 1, Day 7 at the following timepoints: : 0, 1, 2, 4, 6, and 8 hours, Cycle 1, Day 15 at timepoint 0hr and Cycle 1, Day 21 at timepoint 0hr.

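### Neither pill diary's written instructions state the BGJ398 drug-free interval, and the visible grid marks fit neither schedule

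*Combined protocol and SAP*

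**What the plan says.** Section 5.2.3 defines two intermittent schedules: "treatment schedule A (once a day for 21 days on, 7 days off" and "treatment schedule B (once daily for 7 days on, 21 days off) repeating in 28 day cycles". Section 4.2, Section 9.1 and the Phase Ib calendar (Table 9) agree with it. Imatinib is taken every day of the cycle (Section 9.0).

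Section 9.0 introduces the diary: "A pill diary for both medications will be provided and recorded (Appendix B". It gives the purpose as follows: "This will be used to assure compliance with the regimen". The Schedule A diary is Appendix B and the Schedule B diary is Appendix C.

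The two diaries are separate forms, each titled with its schedule, but their special instructions are essentially identical. For BGJ398 both say "Take BGJ398 once a day in the morning". Both then give a missed-dose rule ending in "the missed dose and take the next dose as scheduled". No sentence in either form names an on-day, an off-day or a stop day. Imatinib, which has no break, gets the same once-a-day wording.

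Both grids print an imatinib line and a BGJ398 line for each of Days 1 to 28. Crosses appear on Days 26, 27 and 28 only, in the last capsule-count column, on both drug lines, in both diaries.

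**The concern.** The drug-free interval is what distinguishes Schedule A from Schedule B, and both from continuous dosing. The form given to the patient leaves it out of the instructions and prints lines on which a BGJ398 dose could be entered throughout the interval. It also asks for all missed doses to be recorded, without separating a missed dose from a planned off-day.

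Three things are at stake if a patient takes the form literally.

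- **Dose finding.** Section 9.1 counts DLTs over the 28 days after the first BGJ398 dose. Extra doses in the cycle 1 off-period fall inside that window, so the DLT count behind the MTD and RP2D could reflect a different exposure from the one assigned. The chosen dose and schedule then carry into Phase II.
- **Pharmacokinetics on Schedule B.** Table 10.B takes samples on Days 15 and 21 of cycle 1, both in the off-period. With dosing on those days they would be on-treatment troughs, not levels after stopping.
- **Safety.** Section 3.2.3.1 explains that the 21-on, 7-off schedule came under study because of hyperphosphatemia.

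**Working it through.** The plan states no figure on this point, so there is none to reproduce. The check compares the printed diary lines with the days in Section 5.2.3.

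**Inputs**
- Cycle length 28 days; on-days 21 (A) and 7 (B): Section 5.2.3.
- BGJ398 lines printed per diary: 28 (Appendices B and C, counted).
- Days with a visible cross: 26, 27 and 28, so 3 days in each diary.

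**Off-period lines** = 28 − on-days
- Schedule A: 28 − 21 = 7 lines (Days 22 to 28). Crossed 3; not crossed 7 − 3 = 4 (Days 22 to 25).
- Schedule B: 28 − 7 = 21 lines (Days 8 to 28). Crossed 3; not crossed 21 − 3 = 18 (Days 8 to 25).

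Three crossed days equal neither 7 nor 21. The crosses are the same in both diaries although the off-periods differ, so as they stand they can be correct for at most one schedule, and they are correct for neither.

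**BGJ398 days per cycle if the form alone is followed**, as a ratio to the assigned days

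| Reading of the form | Days | Schedule A | Schedule B |
|---|---|---|---|
| Every printed line dosed | 28 | 28/21 = 1.33 | 28/7 = 4.0 |
| Crossed days skipped | 28 − 3 = 25 | 25/21 = 1.19 | 25/7 = 3.6 |

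These ratios bound a literal reading. They do not predict what patients would do.

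**Position relative to the DLT window.** The window is 28 days, so Days 22 to 28 (A) and Days 8 to 28 (B) lie within it. One limit applies: the phosphorus criterion in Table 3 concerns interruption during the first 21 days of cycle 1. Extra doses on Days 22 to 28 under Schedule A would therefore bear on the other DLT criteria and not on that one.

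**The case against.** The strongest reply has four parts.

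**The grid may be incomplete as seen here.** Shading or crossing-out can be lost when a PDF is converted to text. In the example row the last capsule column holds the BGJ398 count, and that is the column with the crosses. They may therefore be meant to block BGJ398 while leaving the imatinib cell open. All of them also come after the last page break, which would fit capture on one page and loss on the others. Against this, the Day 25 BGJ398 line follows the same page break and shows no cross, although Day 25 is an off-day on both schedules. The question cannot be settled without the original form. A reader might infer that the diaries mark no off-days at all; the documents do not establish that.

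**The instruction is incomplete more than contradictory.** Section 5.2.3 itself uses once-daily wording for dosing days, and the diary defers to a schedule ("the missed dose and take the next dose as scheduled"). This stands in part, but the form never prints the schedule it defers to.

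**Other controls exist.** The dispensing box, with daily dose and capsules given and returned, is marked "Above to be Completed by RN". Section 5.2.3 requires staff to instruct patients and unused drug to be returned each cycle. Section 16.1.1 requires accountability review, and Table 9 schedules a physical exam in each week of cycle 1. A reader might infer that patients will dose through the break, or that the error would go unnoticed. Neither is supported: the first is a risk and not a shown outcome, and capsule counts could reveal excess dosing. They would do so only afterwards, and only when compared with 21 or 7 expected days, which the form does not print.

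**The safety contrast is weak.** Section 11.1.2.1 reports DLTs in 6 patients of an expansion cohort on continuous 125 mg, against 0 of 18 on three weeks on and one off. It states no denominator for the 6, the comparison is not randomised, and the drug was given as monotherapy at 125 mg, whereas this trial starts at 75 mg with imatinib. It is context for why the break exists, not an estimate of the effect of this form.

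**Conclusion.** The point holds in this form: the written instructions in both diaries omit the drug-free interval that defines each schedule, and the visible crosses fit neither off-period. The first half is text and does not depend on how the PDF was converted. The second half is provisional until the original forms are seen.

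For a patient guided by the form alone, the possible excess is 25 to 28 BGJ398 days against 21 on Schedule A (1.19 to 1.33 times) and against 7 on Schedule B (3.6 to 4.0 times). The upper ends assume that every printed line is dosed, the lower ends that the crossed days are skipped, and both assume that enough capsules are in hand and no one intervenes. The existing controls make the excess less likely without making the form consistent with the protocol. The correction is warranted because the form is patient-facing, is the protocol's stated compliance tool, and covers the cycle in which DLTs are counted.

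**What to change.** 1. Check the original Appendix B and Appendix C forms for shading or crossed-out cells that the extracted text does not show.
2. Reconcile both diaries with Section 5.2.3, so that each form's special instructions state in words the on-days and off-days assigned under the schedule in its title.
3. Make the grid marks agree with that schedule, and make clear which drug a mark refers to, so that a planned off-day is not recorded as a missed dose.

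The cost is two revised patient-facing appendices and an IRB submission, with no effect on sample size or data collection. Which dosing rule is right is for the sponsor and investigators to confirm; the request is only that the passages agree.
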